4.4 PATIENT WITHDRAWAL

Patients may withdraw from the entire study at any time without penalty and for any reason without prejudice to her future medical care. Although a patient is not obliged to give her reason for withdrawing prematurely, the PI will make a reasonable effort to obtain the reason while fully respecting the patient's rights. If there is a medical reason for withdrawal, the patient will remain under the supervision of the PI for follow-up of AE(s) as detailed in Section 9.4.1.6. Every effort will be made to continue clinical and/or laboratory follow-up, as appropriate, in patients who wish to withdraw from the study drug (Investigational product or placebo) and reasonable efforts will be made to contact a patient who fails to attend any follow-up appointments, in order to ensure that she is in satisfactory health. A patient's withdrawal of consent and agreement to undergo a final examination will be documented on the electronic case report form (e-CRF).

As far as possible, all assessments scheduled for end-of-treatment must be performed on all patients who receive the study drug but do not complete the study according to protocol. In addition, if patient withdraws from the study, any data collected during the period of time will be maintained as part of the study data.

 Zydus Discovery DMCC	CLINICAL TRIAL PROTOCOL Saroglitazar Magnesium – Phase 2A SARO.17.009	Confidential Page 43 of 82
---	---	-------------------------------

4.4.1 Discontinuation of Patients from the Study or Study Drug

A patient may be discontinued from the study for any of the following reasons:

- Noncompliance to the protocol requirements.
- Occurrence of a serious or intolerable AE and based upon the Investigators' clinical judgment.
- The Sponsor or PI terminates the study (Section 4.6).
- Either the PI or the Sponsor decides that discontinuing the study or discontinuing the patient is in the patient's best interest.
- For reasons related to safety as specified in Section 4.5.
- The patient is lost to follow-up.
- A patient may also be discontinued from study drug/study by the Sponsor, Regulatory Authorities or Institutional Review Board (IRB) or Independent Ethics Committee (IEC).
- If the patient becomes pregnant.

A study completion eCRF, which includes the reason for discontinuation, must be completed for all patients who are discontinued from the study. If the patient is discontinued prematurely, the study completion eCRF should clearly indicate the reason for discontinuation. If the patient discontinues due to an AE, an AE eCRF must be completed. The AE must be followed by medical attention to satisfactory resolution and all study data related to the patient will be reported.

Every effort will be made to continue clinical and laboratory follow-up, as appropriate, in patients who are withdrawn or in whom the study drug is stopped by the PI or per individual stopping rules (Section 4.5).

4.4.2 Patients Lost to Follow-up

Every attempt must be made to have all patients complete the visit schedule. A patient will not be considered lost-to-follow-up unless all efforts to obtain compliance are unsuccessful. Study sites should attempt to contact these patients in order to maintain study visit compliance and all contact attempts should be documented in the patient's medical records. At a minimum, the site should make 2 attempts (at least 3 to 5 days apart and during both business and nonbusiness hours) to contact the patient; once by phone and once by certified mail.

4.5 STOPPING CRITERIA FOR INDIVIDUAL PATIENTS

The following clinical events warrant discontinuation of study drug; however, the patient will continue to be followed for safety, hormonal profile, liver function tests and lipid levels until the event has resolved, i.e., clinical laboratory value(s) has/have returned to baseline or is/are no longer of clinical significance. Discontinuation of study drug will only occur if mandated by safety events as defined below:

Approved by: [name]	Protocol No. SARO.17.009 Version No.: 5.0
------------------------------------	--

 Zydus Discovery DMCC	CLINICAL TRIAL PROTOCOL Saroglitazar Magnesium – Phase 2A SARO.17.009	Confidential Page 44 of 82
--	---	-------------------------------

- Discontinue any patient with an adverse event of Common Terminology Criteria for Adverse Event (CTCAE) grade 3 or higher that is possible or probable drug related and discontinue any patient with an AE of CTCAE grade 4 or higher regardless of attribution to drug.
- Serious AE that may be related to the drug and warrant discontinuation as per discretion of the PI.
- In the opinion of the PI, continuation of study drug poses a health risk to the patient.
- Evidence of drug induced liver injury requiring study drug discontinuation as shown in the algorithm below.
- The second LFTs [AST, ALT, ALP, GGT, serum protein, albumin and total bilirubin (with conjugated bilirubin)] values during the Screening Phase (those obtained at Visit 2) will be considered as baseline for the safety assessment.
 - If patients with abnormal baseline liver indices develop elevations of AST or ALT greater than 2 times baseline or total bilirubin greater than 1.5 X baseline values (BL) while on study, testing should be repeated within 48-72 hours. If there are persistent elevations in ALT or AST greater than 2 X baseline or TB greater than 1.5 X baseline values, then close observation (see DILI Guidance for definition, testing and physical examination 2-3 times per week) should be initiated or drug should be discontinued.
 - A decision to discontinue or temporarily interrupt a study drug should be considered based on factors that include how much higher baseline ALT and AST were relative to the upper limit of normal (ULN) and how much the on study ALT and AST levels have increased relative to baseline, in addition to whether there is concomitant elevation of bilirubin or INR.
 - The criteria for discontinuing or temporarily interrupting study drug are as follows:
 - When the baseline values were ≥ 1.5 X ULN but < 5 X ULN, discontinue if ALT or AST increases to > 3 X baseline.
 - Discontinue if ALT or AST increase > 2 X baseline and the increase is accompanied by a concomitant TBL increase to > 2 X baseline or the INR concomitantly increases by > 0.2 .
 - Discontinue and evaluate any patient with elevations of ALT/AST if sign or symptoms of right upper quadrant pain, abdominal pain, anorexia, nausea, vomiting fever, eosinophilia and/or rash are present.
 - If a patient lives in a remote area, they can be tested locally and the results be communicated to the investigator site promptly.

 Zydus Discovery DMCC	CLINICAL TRIAL PROTOCOL Saroglitazar Magnesium – Phase 2A SARO.17.009	Confidential Page 45 of 82
---	---	-------------------------------

- Total CK > 5X ULN
- Amylase or lipase > ULN
- eGFR < 60 ml/min/1.73 m² and where the value is reconfirmed after 24 hours. Additionally, any subject who requires renal replacement therapy should also be discontinued from drug.
- Complete Blood Counts: Hemoglobin < 10 g/dL or HCT < 30%; platelets < 100,000/microL; WBC < 4 x 10⁹/L.

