4.6 TERMINATION OF THE CLINICAL STUDY

If the Investigator, the Sponsor or the Medical Monitor becomes aware of conditions or events that suggest a possible hazard to patients if the clinical study continues, then the clinical study may be terminated after appropriate consultation among the involved parties. Also, the clinical study may be terminated at the Sponsor's discretion in the absence of such a finding. Conditions that may warrant termination of the clinical study include, but are not limited to:

- The discovery of an unexpected, relevant or unacceptable risk to the patients enrolled in the clinical study;
- Three patients develop the same AE of CTCAE grade 3, considered to be at least probably related to study drug;
- Two patients develop any AE of CTCAE grade 4, considered to be at least probably related to study drug;
- One patient develops an AE of CTCAE grade 5, considered to be at least probably related to study drug;
- Failure to enroll patients at the required rate;
- A decision of the Sponsor to suspend or discontinue development of the study drug.

Should the study be terminated and/or the site closed for whatever reason, a copy of all documentation pertaining to the study and study drugs must be returned to the Sponsor. All the site specific documents will be archived at study site.

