9.4.1.4 Assessment of Adverse Events

Each AE will be assessed by the PI with regard to the following categories:

Severity

Approved by: [name]	Protocol No. SARO.17.009 Version No.: 5.0
------------------------------------	--

 Zydus Discovery DMCC	CLINICAL TRIAL PROTOCOL Saroglitzaz Magnesium – Phase 2A SARO.17.009	Confidential Page 71 of 82
---	--	-------------------------------

The PI will provide an assessment of the severity of each AE by recording a severity rating on the appropriate AE reporting page of the patient's eCRF. Severity will be assessed according to the following scale:

Mild: Event is usually transient and easily tolerated, requiring no special treatment and causing no disruption of the patient's normal daily activities.

Moderate: Event introduces a low level of inconvenience or concern to the patient and may interfere with daily activities, but is usually improved by simple therapeutic measures. Moderate experiences may cause some interference with functioning.

Severe: Event interrupts the patient's normal daily activities and generally requires systemic drug therapy or other treatment. Severe events are usually incapacitating.

Causality

For all AEs, the PI will provide an assessment of causal relationship to study drug. The causality assessment must be recorded on the appropriate AE reporting page of the patient's eCRF.

Causal relationship will be classified according to the following criteria:

- Unrelated
- Possibly related: Suggests that the association of the AE with the study drug is unknown. However, the AE is not reasonably supported by other conditions.
- Probably related: Suggests that a reasonable temporal sequence of the AE with study drug administration exists and, based upon the PI's clinical experience, the association of the AE with study drug seems likely.
- Definitely related: Suggests that a causal relationship exists between the study drug and the AE, and other conditions (concomitant illness, progression or expression of the disease state, reaction to concomitant medication) do not appear to explain the AE.
- Unknown

Outcome

Outcome of AEs will be defined according to the ICH topic E2B, ICH Guideline, as follows:

- Recovered/Resolved
- Recovered/Resolved with sequelae
- Recovering/Resolving
- Not Recovered/Not Resolved
- Fatal
- Unknown

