9.4.1.5 Recording Adverse Events

Approved by: [name]	Protocol No. SARO.17.009 Version No.: 5.0
------------------------------------	--

 Zydus Discovery DMCC	CLINICAL TRIAL PROTOCOL Saroglitazar Magnesium – Phase 2A SARO.17.009	Confidential Page 72 of 82
---	---	-------------------------------

All AEs must be recorded on the appropriate AE eCRF for the patient. All AEs must be reported whether or not considered causally related to study drug. For every AE, the PI will provide an assessment of the severity and causal relationship to study drug, will document all actions taken with regard to study drug, and will document any other treatment measures for the AE. If an outcome for an AE is not available at the time of the initial report, follow-up will proceed until an outcome is known.

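### Read literally, the mandatory grade 3 stopping rule in Protocol 4.5 omits AEs rated definitely related; those meeting no laboratory or liver trigger are stopped only by judgement

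*Protocol*

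**What the plan says.** Protocol 4.5 introduces its list of individual stopping criteria with the statement "Discontinuation of study drug will only occur if mandated by safety events as defined below". The first bullet has two parts. An AE of CTCAE "grade 3 or higher that is possible or probable drug related" leads to discontinuation, and so does any AE of grade 4 or higher regardless of attribution.

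Two further bullets in 4.5 rest on judgement: "Serious AE that may be related to the drug and warrant discontinuation as per discretion of the PI" and "In the opinion of the PI, continuation of study drug poses a health risk to the patient". The rest of the list consists of liver criteria and laboratory limits (CK, amylase or lipase, eGFR, blood counts), none of which depends on causality.

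Protocol 9.4.1.4 gives the investigator five causality ratings: unrelated, possibly, probably and definitely related, and unknown. The strongest is defined as "Definitely related: Suggests that a causal relationship exists between the study drug and the AE".

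Protocol 4.4.1 lists reasons for which a patient may be discontinued, including "Occurrence of a serious or intolerable AE", subject to clinical judgement.

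Protocol 4.6, on terminating the whole study, uses threshold wording. One of its conditions is "Three patients develop the same AE of CTCAE grade 3, considered to be at least probably related to study drug"; its grade 4 and grade 5 conditions use the same attribution phrase.

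**The concern.** A stopping rule should be at least as strict for a stronger attribution as for a weaker one. As written, the grade 3 rule names two of the three related levels and leaves out the strongest. A site applying the text word for word must stop drug for a possibly related grade 3 event, but finds no such instruction in that bullet for one the investigator is sure the drug caused.

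The wording carries weight because the lead-in presents the list as the complete set of grounds, and because other sections depend on it. Section 4.4.1 cites 4.5 as a reason for discontinuation, and 7.5 counts failure to withdraw a patient who met withdrawal criteria as a deviation. Under a literal reading, a monitor could cite the grade 3 bullet against continued dosing after a possibly related event but not after a definitely related one. What is at stake is patient safety, on a narrow class of events.

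**Working it through.** No sample size, power or alpha figure bears on this point, so there is no stated figure to reproduce. The check compares the rule with the causality scale and then looks for other routes to a stop.

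**Step 1: the AE bullet of 4.5 against the scale in 9.4.1.4, read literally.**

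| Causality rating (9.4.1.4) | Grade 3: stop mandated? | Grade 4 or higher: stop mandated? |
|---|---|---|
| Unrelated | No (appropriate) | Yes |
| Possibly related | Yes | Yes |
| Probably related | Yes | Yes |
| Definitely related | **Not named** | Yes |
| Unknown | Not named | Yes |

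The gap is confined to grade 3, because the second half of the bullet covers everything above it. *Unknown* is also unnamed at grade 3. That is less plainly a mistake, but the protocol should say what is meant.

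**Step 2: other routes for a definitely related grade 3 AE.**

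- *Objective routes in 4.5, whatever the attribution:* ALT or AST above 3 times baseline where baseline was at least 1.5 but below 5 times ULN; ALT or AST above 2 times baseline with bilirubin above 2 times baseline or an INR rise above 0.2; raised ALT or AST with listed symptoms or signs; CK above 5 times ULN; amylase or lipase above ULN; confirmed eGFR below 60 or need for renal replacement; haemoglobin, haematocrit, platelet or white cell limits. An event meeting one of these does not depend on the AE bullet.
- *Judgement routes:* the serious-AE bullet (investigator discretion), the health-risk bullet (investigator opinion), and 4.4.1 (a patient may be discontinued). None requires a stop from grade and attribution alone.

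What remains uncovered by any mandatory rule is a definitely related AE of exactly grade 3 that meets no laboratory or liver criterion. Many non-laboratory clinical events would fall here.

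**Step 3: comparison with 4.6.** All three AE-based termination conditions (grades 3, 4 and 5) set a floor for attribution and so include the strongest level. Taken literally, three patients with the same definitely related grade 3 AE may warrant ending the trial, yet the grade 3 rule of 4.5 names none of them. Threshold wording was therefore available to the authors and was not used in 4.5.

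**Step 4: whether planned outputs would show such cases.** SAP 9.8.1 plans a listing of all AEs, but its tables give strongest relationship and maximum severity separately. A definitely related grade 3 AE after which dosing continued would not be identifiable from those tables, nor from the table of TEAEs leading to permanent discontinuation.

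**The case against.** The best reply is that the literal reading is strained. Section 4.5 says possible or probable, which are not the exact labels of 9.4.1.4, and it does not refer to that section. An event that the drug certainly caused would ordinarily also satisfy the definition of probably related, so most investigators would take the phrase as a floor. The lead-in is less restrictive than it looks, since the health-risk bullet is itself a listed criterion and 4.4.1 adds further grounds. The causality rating that triggers the grade 3 rule is also the investigator's own judgement. Finally, 4.6 is permissive and operates at study level, so its different wording is not in itself a conflict, and the mismatch appears only once the literal reading of 4.5 is accepted.

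Most of this stands as an account of intent and of likely practice, and it is why the point is minor. It does not remove the defect. The protocol defines *Definitely related* as its own level, the mandatory rule does not name it, and 4.6 shows how the authors worded a floor elsewhere. The judgement routes permit a stop; they do not require one.

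A reader might go further and infer that definitely related AEs in general can be stopped only by judgement, or that 4.5 prevents stopping them. The documents support neither. Grade 4 and above is always stopped, the laboratory and liver criteria apply whatever the cause, and the health-risk bullet allows a stop whenever the investigator holds that opinion.

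**Conclusion.** The point holds as a minor safety wording error: the mandatory grade 3 rule, followed as written, leaves out the strongest attribution, and the omission bites only for events of exactly grade 3 that meet no objective criterion in 4.5. It is almost certainly a drafting slip for at least possibly related.

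The conclusion rests on two assumptions: that the words in 4.5 correspond to the rating levels of 9.4.1.4, and that a site might follow them literally. The number of women affected cannot be computed, because the documents give no rate of grade 3 events or of definite attributions; the practical effect is expected to be small. Counting the grade and causality combinations left out would describe the wording, not the risk.

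A reader might also infer that the omission distorts the per-protocol set or the primary comparison through who stops drug. Nothing in the documents supports that, and no effect on the efficacy analysis is claimed.

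**What to change.** Reword the first bullet of 4.5 to: *CTCAE grade 3 or higher that is at least possibly related to study drug (possibly, probably or definitely related)*. Add a sentence on how a grade 3 AE rated *Unknown* is treated, since the new wording alone does not settle that. The cost is a line or two in a protocol amendment or a clarification letter to sites.

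The documents do not say whether dosing has ended; SAP 7.3 says only that recruitment is to close at 60 participants. If it has ended, filter the AE listing planned in SAP 9.8.1 for grade 3 AEs rated definitely related and report them in the clinical study report with the action taken on study drug. The information is already collected: under Protocol 9.4.1.5 the investigator assesses severity and causality for every AE and "will document all actions taken with regard to study drug", and SAP 9.8.1 refers to CTCAE grade. The cost is one filter, provided the listing shows grade, relationship and action taken.

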4.6 TERMINATION OF THE CLINICAL STUDY

If the Investigator, the Sponsor or the Medical Monitor becomes aware of conditions or events that suggest a possible hazard to patients if the clinical study continues, then the clinical study may be terminated after appropriate consultation among the involved parties. Also, the clinical study may be terminated at the Sponsor's discretion in the absence of such a finding. Conditions that may warrant termination of the clinical study include, but are not limited to:

- The discovery of an unexpected, relevant or unacceptable risk to the patients enrolled in the clinical study;
- Three patients develop the same AE of CTCAE grade 3, considered to be at least probably related to study drug;
- Two patients develop any AE of CTCAE grade 4, considered to be at least probably related to study drug;
- One patient develops an AE of CTCAE grade 5, considered to be at least probably related to study drug;
- Failure to enroll patients at the required rate;
- A decision of the Sponsor to suspend or discontinue development of the study drug.

Should the study be terminated and/or the site closed for whatever reason, a copy of all documentation pertaining to the study and study drugs must be returned to the Sponsor. All the site specific documents will be archived at study site.

5 STUDY TREATMENTS / INVESTIGATIONAL PRODUCT MANAGEMENT

Saroglitazar Magnesium 4 mg Tablets or placebo will be administered in patients of PCOS with NAFLD once daily in the morning before breakfast without food, for a period of 24 weeks.

5.1 TREATMENTS TO BE COMPARED

5.1.1 Investigational Product Description

The products that will be used in this study are outlined in Table 2.

A 5x5 grid of black bars. The bars are of varying lengths, creating a visual representation of data. A horizontal line runs through the center of the grid, intersecting the bars. The bars are arranged in a grid pattern, with some bars being longer than others, indicating a range or distribution of values.

5.1.2 Comparator Drug Description

Placebo will be used as comparator, which will be formulated as tablets, and will contain above mentioned excipients without Saroglitzaz Magnesium Micronized (Refer section 5.1.1 for excipients details). The IP will be manufactured following current-Good Manufacturing Practice (cGMP) guideline.

5.2 DOSAGE AND TREATMENT SCHEDULE

Patients will receive either 4 mg Saroglitazar Magnesium or placebo orally once each morning before breakfast without food, for 24 weeks during the double-blinded treatment period. However, on scheduled visits patients will have the IP administered on site after the blood sample collection. The drug dose during the treatment phase, this will be checked and verified with study medication compliance by using drug accountability form.

Approved by: [name]	Protocol No. SARO.17.009 Version No.: 5.0
------------------------------------	--

 Zydus Discovery DMCC	CLINICAL TRIAL PROTOCOL Saroglitazar Magnesium – Phase 2A SARO.17.009	Confidential Page 48 of 82
--	---	-------------------------------

5.3 PACKAGING, LABELLING AND SUPPLY

Study drug will be packaged by the Sponsor according to all local legal requirements. [REDACTED]

[REDACTED]

[REDACTED]

[REDACTED]

[REDACTED]

An adequate quantity of study drug will be shipped to each site. The PI will maintain an accurate record of the receipt of the study drug, including the date received. Until dispensed to the patients, the study drug will be stored at room temperature (20°C to 25°C or 68°F to 77°F) in a dry place at the study site or pharmacy that can be securely locked and that is accessible to authorized personnel only.

